## **10. Statistical Analysis**

Power of the study will be fixed at 80% ( $\beta=0.20$ ) just as was used in calculation for necessary sample size, with  $\alpha = 0.05$  as the significance level. Data will be entered into SPSS Statistics or

another secured data collection system and data will be analyzed. Information will be stored on a password protected computer using an encrypted file and will be maintained as confidential protected health information (PHI). Examiners will be trained at the start of the study and calibrated on the use of the ICDAS criteria, and on the clinical outcome variables using extracted teeth to determine intra and inter-examiner reliability (dentin color, dentin hardness, and lesion size in mm), which will be measured with kappa statistics. A Chi-square test will be applied to determine if there is a difference in distribution of variables such as age, gender, brushing habits, fluoride exposure, etc. Chi-square tests will also be used to determine differences in dropout rates, failure rates, patient satisfaction/acceptance, and overall cost. The primary outcome, the proportion of children reporting major failures during the 12 month follow up period, will be analyzed using a mixed model with a binomial error structure. We will also analyze minor failures in a similar manner. The dependent variables will be a binary indicator of major failure, with differences between study treatments fitted as fixed effects. Estimates of the relative risk of major failure in the two groups will be presented in the form of odds ratios and associated 95% confidence intervals. Within this framework we will be able to estimate:

1. The mean difference between groups at the end of the follow up period;
2. The mean difference between groups across the whole of the follow up period; and
3. The difference in the rate of change of the outcome across the follow up period

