## 6. Study Visits and Intermediate Contacts

Recalls for both groups will occur via phone questionnaire as well as follow-up visits. Participants will be contacted at 1 month, 2 months, 4.5 months and 9 months ( $\pm$  2 weeks) following restoration placement or application of SDF. Subjects will need to present to the clinic for follow-up visits at 3 months ( $\pm$  6 weeks), 6 months ( $\pm$  6 weeks), and for study completion at 12 months ( $\pm$  6 weeks) (Table 1). Subjects will also be called to schedule and confirm these follow-up visits; these short calls will require no payment to the study subjects. In the case of an emergency, an emergency visit will be scheduled at Mott Children's Health Center or the University of Michigan School of Dentistry. An emergency will be evaluated and treated according to the AAPD guidelines, followed by completion of appropriate case report forms (CRFs) and reporting to IRBs and study sponsors (Appendix 10, CRF 14-17). In the event of minor or major failure in either study group, the subject will be withdrawn from the study and teeth will be given the appropriate treatment as stated in the AAPD Guidelines free of charge, these teeth will be categorized as a failure, and a *CRF 04 Treatment Deviation CRF (Appendix 10, CRF 04)* will be completed.

**Table 1.** Patient Contact Interval

Patient Contact	Recall Interaction	Time Scale
Clinic Visit #1	Consent/Accent, baseline questionnaires, initial caries assessment, radiographs*, intervention	T = 0
Intermediate Contact	Attrition prevention, update contact information, follow-up on pain	T = 1 month, 2 months (Additional reminder for Clinical Visit #2)
Clinic Visit #2	Assessment for major and minor failure & assessment of pain and parent satisfaction	T = 3 months
Intermediate Contact	Attrition prevention, update contact information, follow-up on pain	T = 4.5 months (Additional call reminder for Clinical Visit #3)
Clinic Visit #3	Reapplication of SDF in that group; Assessment for major & minor failure, radiographs*, and assessment of pain and parent satisfaction	T = 6 months

Intermediate Contact	Attrition prevention, update contact information, follow-up on pain	T = 9 months (Additional call for scheduling/reminder for Clinical Visit #4)
Clinic Visit #4	Assessment for major & minor failure, radiographs*, and final questionnaires	T = 12 months

\* Radiographs will be obtained only if an existing radiograph within 30 days of the visit is not available.

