### 7.2. Clinical Variables

At the baseline visit the study teeth carious lesions will be assessed based on size (mm), dentin color (yellow, brown, black), dentin hardness (soft - any explorer penetration of dentin when very light force is applied or hard – no dentin penetration when using an explorer with very light force), and periapical radiographs (outer/middle/inner third of dentin, major/minor failure criteria). All information will be noted on the respective *CRF Intervention Visit* by the provider prior to treatment. These clinical characteristics will also be recorded for the SDF groups at follow-up visits (as the lesion is exposed clinically). Recall clinical visits will involve assessment of the lesion based on minor and major failure criteria (Table 2). All assessments will be noted on the respective *CRF 3 & 6 Month* (Appendix 10, CRF 10 & 11) or on the *CRF 12 Month* at the patient's 12 month recall (Appendix 10, CRF 12 & 13). Both groups will have periapical radiographs taken at the baseline and 6 and 12 month recalls (and at any other time if deemed clinically necessary). If a radiograph from within 30 days of the visit is available, a radiograph will not be taken at the study visit unless deemed clinically necessary. De-identified clinical photos will also be taken as deemed necessary for research and publication purposes, with parental consent. Length of time and cost for each intervention will be calculated and analyzed for comparison.

**Table 2.** Major and Minor Failure Criteria

	SDF Application	Conventional Restoration
Success	
 
• Caries arrested – dentin feels hard to explorer
 
• No clinical signs or symptoms of pulpal pathology
 
• Tooth exfoliated without major or minor failure
 
	
 
• Restoration appears satisfactory
 
• No clinical signs or symptoms of pulpal pathology
 
• Tooth exfoliated without major or minor failure
 

Minor Failure	
 
• Caries progression – soft dentin, increase in lesion size clinically or radiographically
 
• Reversible pulpitis to be treated without pulpotomy or extraction
 
	
 
• Secondary caries
 
• Restoration fracture or wear requiring repair
 
• Loss of restoration
 
• Reversible pulpitis to be treated without pulpotomy or extraction
 

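### Kappa is planned for lesion size in millimetres, so the calibration gives no measurement error for a size item that counts towards SDF minor failure

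*Combined protocol and SAP*

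**What the plan says.** Section 10 (Statistical Analysis) has examiners calibrated on extracted teeth. Intra- and inter-examiner reliability covers "dentin color, dentin hardness, and lesion size in mm), which will be measured with kappa statistics". It names no weights, size categories, rounding unit, ICC, standard deviation or limits of agreement.

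Lesion size also enters an outcome. In Table 2 (Section 7.2) the first SDF minor-failure item is "Caries progression – soft dentin, increase in lesion size clinically or radiographically", with no minimum change. The SDF success row asks for "Caries arrested – dentin feels hard to explorer" and for no pulpal signs or symptoms, and does not mention size. The conventional column has no size item. Its minor-failure items include secondary caries and "Restoration fracture or wear requiring repair".

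Section 7.2 also says: "These clinical characteristics will also be recorded for the SDF groups at follow-up visits (as the lesion is exposed clinically". No such re-recording is planned for the conventional arm.

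Section 6 sets the consequence: "In the event of minor or major failure in either study group, the subject will be withdrawn from the study". The tooth is then categorised as a failure. Clinic recalls fall at 3, 6 and 12 months.

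Section 10 makes major failure the primary outcome and analyses minor failure in a similar way.

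**The concern.** The calibration exercise is the only planned source of information on how precisely lesion size is read. Kappa asks how often two readings fall in the same category, beyond chance. Without weights, a 1 mm disagreement counts the same as a 5 mm one. With any weights, the result is a unitless index and not an error in millimetres. When a lesion reads larger at recall than at baseline, the trial will therefore have no figure for judging whether the difference exceeds reading error.

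That would be a small matter if size were only descriptive. It is instead a minor-failure item with no stated minimum, re-recorded in one arm, read by unblinded assessors (Section 4.4). Five or six residents at each of two sites do the screening, treatment and recall (Section 11), so baseline and recall readings may come from different people. Section 11 lists provider calibration for color and hardness and does not mention size.

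Two things are at stake: the SDF minor-failure rate, and the follow-up of children withdrawn after a minor failure that may be only a reading difference. Withdrawal also ends their observation for major failure.

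**Working it through.** The plan states no figure for size reliability or measurement error, so there is none to reproduce. The sample size of 68 (98 with attrition) is not affected.

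**Inputs.** From the documents: three recalls, no minimum size change, no rounding unit. Assumed, because the documents give nothing: true sizes Normal with mean 4 mm and SD 1 mm; independent Normal reading error with SD 0.3, 0.5 or 0.7 mm; readings to the nearest mm. The figures come from simulations of at least 400,000 lesions.

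**1. Kappa against ICC.** Rounding to whole mm adds variance of about 1/12 = 0.083.
- ICC = 1 / (1 + SD² + 0.083). At SD 0.5: 1 / (1 + 0.25 + 0.083) = 0.75.
- Unweighted kappa = 1 − observed disagreement / chance disagreement. At SD 0.5: 1 − 0.514 / 0.756 = 0.32.
- On the same readings, linear-weighted kappa is 0.55 and quadratic-weighted kappa is 0.75, equal to the ICC.

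Unweighted kappa also depends on the recording unit. With error SD 0.5 mm it is 0.32, 0.17 or 0.03 for readings to 1, 0.5 or 0.1 mm, although the examiners are equally precise.

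**2. False increases if size alone triggers failure.** There is no true growth, and one baseline reading is compared with three recall readings.

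| Error SD (mm) | Unweighted kappa | ICC | Reads ≥1 mm larger at any recall | Reads ≥2 mm larger at any recall |
|---|---|---|---|---|
| 0.3 | 0.55 | 0.85 | 31% | 0.4% |
| 0.5 | 0.32 | 0.75 | 45% | 6% |
| 0.7 | 0.19 | 0.64 | 54% | 16% |

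At error SD 0.5 mm the figure for a single recall is 26%. A wider grid (rounding 0.1 to 1 mm, error SD 0.25 to 0.75 mm, true SD 1.0 to 1.5 mm) gives 26–73% over three recalls.

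**3. What an error in mm would supply.** Smallest detectable change = 1.96 × √2 × √(SD² + 0.083).
- SD 0.3: 2.772 × 0.416 = 1.15 mm
- SD 0.5: 2.772 × 0.577 = 1.60 mm
- SD 0.7: 2.772 × 0.757 = 2.10 mm

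On the wider grid, counting only increases beyond this value lowers the three-recall figure to 0–10%.

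**4. What such a cut loses.** With true growth of 1 mm present at all three recalls, a 2 mm cut never flags the lesion in 69%, 55% or 46% of children (error SD 0.3, 0.5, 0.7). At SD 0.7 the smallest detectable change exceeds 2 mm, so whole-mm readings would need 3 mm.

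**5. Table 2 side by side.** A lesion that is hard but reads larger meets the arrested-caries item for success and also the size item for minor failure. The text does not say whether softness and size are separate or joint signs of progression. The figures in step 2 apply only if they are separate.

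**The case against.** The strongest reply is that this is a calibration detail. The kappa on extracted teeth enters no treatment comparison, the plan does not exclude weighted kappa, and quadratic weights would equal the ICC. That stands against the claim that kappa always understates reliability. It does not answer the lack of an error in mm, which holds for every form of kappa.

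A reader might infer that any size increase is automatically a failure. The documents do not support this. The Table 2 item is caries progression, with softness and size both named as signs; nothing says that two readings are subtracted mechanically. If both signs are required, the false-failure rate is lower than in the table above. The follow-up case report forms are not in the text reviewed and might say more.

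A reader might also infer a one-way bias against SDF. The size item is confined to that arm, but the conventional arm has judgement items without thresholds, such as secondary caries and wear needing repair, and both arms have 6- and 12-month radiographs. False failures from those items have not been estimated. Some arm-specific criteria are unavoidable when a restoration covers the lesion.

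Nor does the point reach the definition of the primary outcome. Major failure contains no item for a measured size increase.

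Finally, writing a minimum size change into Table 2 would alter when a child is withdrawn and the tooth treated. That is a clinical rule and is not proposed here.

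**Conclusion.** The concern holds in limited form. Kappa is the wrong summary for a millimetre measurement: without weights it understates agreement (0.32 against 0.75 in the central example), and with any weights it gives no measurement error. The gap matters because an increase in size with no stated minimum is an SDF minor-failure item, size is re-recorded only in that arm, and a minor failure ends participation.

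If size alone can trigger failure, about 31–54% of unchanged lesions would read at least 1 mm larger at some recall. This rests on whole-mm readings and error SDs of 0.3–0.7 mm, all assumed; it shows possible scale and is not an estimate for this trial. The affected outcome is minor failure, not the primary outcome. The direction and size of any net bias between arms are not established.

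**What to change.** 1. In Section 10, keep kappa for color and hardness. For lesion size, report the ICC, the within-examiner and between-examiner SD in mm, and the smallest detectable change, all from the calibration already planned. State the recording unit.

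2. Add a sensitivity analysis of minor failure in which SDF failures based only on a size increase within measurement error are not counted. Clinical management stays as it is. Because those children will have been withdrawn, the analysis should state how their later status is handled, for example as missing from that visit.

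3. The sponsor should reconcile the success and minor-failure rows of Table 2 for a lesion that is hard but reads larger, and state whether softness and size are joint or separate criteria. The case report form should record which sign led to each failure; without that, size-only failures cannot be identified.

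The cost is some wording and a little extra analysis, with no new patients or visits and no change in sample size. There are two drawbacks. Error measured on extracted teeth may be smaller than error in children, so the sensitivity analysis may remove too few false failures. It may also discount some true small growth, as step 4 of the working shows, so it should stand beside the main minor-failure analysis and not replace it.

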## **2. Objectives**

The objectives of this clinical study are to evaluate:

- The effectiveness of treatment of cavitated caries in children by application of silver diamine fluoride (SDF) in comparison to conventional restorative treatments
- The perceptions of parents and patients to both treatment modalities and their levels of acceptability
- The opinions of dental providers in terms of ease of use and clinical time spent
- The relative cost-effectiveness of the two treatment approaches regarding both practitioner chair time and material-based cost

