### **3.6. Current Research**

According to Rosenblatt et al., the advantages of SDF are numerous. While it can control the infection, it is also easy to use, highly affordable, involves minimal chair time, and is quite non-invasive. They also concluded there is no [published] research that addresses all of these topics. SDF was approved in the United States in July 2014 and currently there have been no clinical trials in the United States testing the application of SDF to arrest caries in children. Also, there seem to be no studies that address the failure rates of SDF in comparison to conventional one and two-surface restorations for the treatment of dentin caries. The researchers' aims in this study will be

to address affordability, ease of use, and both patient/parent and provider acceptance, in addition to clinical success rates when compared to conventional restorations.

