## **4. Materials and Methods**

### **4.1. Purpose**

To determine the effectiveness of the application of silver diamine fluoride (SDF) in comparison to conventional restorative treatments in International Caries Detection and Assessment System criteria (ICDAS) 5 and 6, one and two surface carious lesions in primary molars which will be assessed based on major and minor failure criteria when followed for one year. Additionally, parents'/children's and providers' perceptions will be assessed as well as the cost of both regimens, to include both chair time spent and materials' costs.

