### **4.2. General Outline**

Children, 2-10 years of age will be invited to participate. The original study site is Mott Children's Health Center (MCHC) in Genesee County, Michigan. Following a slow recruitment period, the University of Michigan School of Dentistry (UMSOD) Children's Clinic was added as a second study site. Given the current data in the literature, the combined failure rate for conventional restorative techniques (e.g. compomers) is approximately 29% at one year follow-up, while application of silver diamine fluoride has a failure rate of 63% at one year follow-up, with increased success over time. Although the failure rate of SDF at one-year follow-up seems alarming, as indicated by Zhi, *et al.* it may be possible to increase the success rate with additional applications providing success rates up to 90.1% at 24 months. Using these data,  $\alpha$ -value of 0.05 and a Power set at 80%, the resulting sample size would be 68 (34 per group) as calculated using the software, nQuery (Appendix 1). To account for 30% attrition, the final number needed for the initial study will be 98 (92 for 25% attrition, 86 for 20% attrition). Subjects will be contacted by phone regularly and invited to two intermediate clinic visits (plus a final study visit) to reduce attrition (Table 1). Given a review of the current literature of the few Randomized Controlled Clinical Trials involving SDF worldwide, the majority of this research has been completed with pre-school aged children. Almost all research discusses arresting or prevention of caries in the

primary dentition, as well as prevention of caries on first permanent molars. Due to the strength of the current research, this study will be focused on the primary dentition of children in the U.S. These children and their parents will be approached when presenting for examination/recall/or treatment at Mott Children's Health Center, Flint, MI, or the University of Michigan School of Dentistry Children's Clinic, Ann Arbor, MI. Interested families with children that qualify following screening examination will be provided with an *Informed Consent/Assent* (Appendix 3) and an *Enrollment Information Form* (Appendix 4).

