### **5.2. SDF management of caries**

- The selected tooth with notable decay into dentin will be isolated with cotton rolls.
- No caries removal will be performed, except for food or other obvious debris.
- Tooth will be dried with gauze and SDF solution will be placed on the carious dentin until it is saturated.
- Excess SDF will be blotted dry with a cotton pellet.
- A second application of SDF solution will then be placed to ensure that the entire carious surface is wetted, and excess will again be blotted with a cotton pellet.
- Following the second application of SDF, the area will be isolated for 3 minutes to allow for ample drying before allowing contact with saliva and soft tissues
- Should the SDF come in contact with any soft tissues, soft tissue should immediately be wiped with a saline wipe
- Following completion of the SDF intervention visit, the provider will complete the CRF 03 *Intervention Visit: Silver Diamine Fluoride* CRF (Appendix 10, CRF 03).
- A second application of SDF will be applied at 6 month recall, following the same protocol as noted above (Due to the potential for increased caries arrest rate with a 6 month application).
- Any new carious lesions that develop after the initial treatment will be recorded, and treated using conventional treatment methods and will not be included in the study.
- Following the completion of this study, teeth in the SDF group will be treated according to AAPD guidelines or observed for exfoliation. The parent of an SDF treated child can elect a restoration following AAPD guidelines at the 12 month visit.

Both groups will receive the following, according the standard procedures at the MCHC/UMSOD:

- Oral Health Instruction (OHI) and diet instruction
- Tooth brushing/dentifrice use at home
- Fissure sealants for permanent teeth will be placed if deemed necessary.
- Traditional preventative care at recalls based on AAPD guidelines (Regular recall exams, prophylaxis, scaling, flossing, and fluoride varnish at 6 month recalls will be provided for both treatment arms. Special care will be taken to not apply fluoride varnish directly to the carious lesion which is being treated with SDF.)

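### Section 10 assigns a chi-square test to overall cost, which needs cost bands the plan does not define and yields no between-arm cost difference or interval

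*Combined protocol and SAP*

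**What the plan says.** Section 10 names one analysis for cost: "Chi-square tests will also be used to determine differences in dropout rates, failure rates, patient satisfaction/acceptance, and overall cost". Cost shares that sentence with dropout, failure and satisfaction.

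The economic aim is in Section 2: "The relative cost-effectiveness of the two treatment approaches regarding both practitioner chair time and material-based cost". Section 4.1 likewise promises "the cost of both regimens, to include both chair time spent", together with the cost of materials. Section 7.2 adds: "Length of time and cost for each intervention will be calculated and analyzed for comparison". Section 7.4 bases the economic evaluation on time and materials. None of these sections gives cost categories, unit costs, an estimator or an interval.

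The 95% intervals in Section 10 are for odds ratios of major failure. The mean differences listed at the end of that section are set within the binomial model for failure, so they do not cover cost.

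On data capture, Section 7.3 says that the time to complete a baseline visit is recorded for each intervention, on the intervention-visit forms. Section 5.2 adds, for the SDF arm: "A second application of SDF will be applied at 6 month recall, following the same protocol as noted above".

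**The concern.** The first three items in the chi-square sentence are categorical, or can easily be made so. Cost is not. To apply the test, the analyst must cut cost into bands. With no bands in the plan, they would be chosen later, possibly with the data in view, and the p-value would depend on that choice.

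The larger loss is the missing estimate. Cost-effectiveness sets a difference in cost against a difference in outcome. Section 4.2 plans on one-year failure of 63% with SDF and 29% with conventional restoration. A reader will therefore want to know how much is saved per child, with what uncertainty, and against how many more failures. A banded test answers none of this. Section 3.6 already reports, from a cited review of SDF: "While it can control the infection, it is also easy to use, highly affordable, involves minimal chair time". Showing only that the arms differ in cost would add little to that.

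**Working it through.** **The plan's own figures.** The documents state no figure for cost, so there is none to reproduce. The per-arm numbers come from Section 4.2. The plan needs 68 children, so 68/2 = 34 per arm. For attrition, 34/(1 - 0.30) = 48.6, rounded up to 49 per arm, or 98 in total. This matches the plan: "To account for 30% attrition, the final number needed for the initial study will be 98".

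**Does the test fit the variable?** Sections 2, 4.1 and 7.4 build cost from time and materials, which is a quantity. Section 10 applies a test for counts in categories. No section links the two by defining bands.

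**How much do the bands matter?** The documents give no mean or SD for cost, so what follows is an illustration. The assumptions are normal costs, equal SD in both arms, bands cut at pooled-sample quantiles, an uncorrected chi-square test and a two-sided 5% level. The 0.69 SD difference is chosen because a comparison of means then has about 80% power with 34 per arm. Simulated power:

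| Per arm | Difference | Welch t-test | 2 bands | 3 bands | 4 bands |
|---|---|---|---|---|---|
| 34 | 0.69 SD | 79.8% | 51.6% | 54.1% | 54.1% |
| 49 | 0.69 SD | 92.4% | 74.9% | 76.9% | 73.2% |
| 34 | 1.5 SD | 100% | 99.6% | 99.9% | 99.8% |

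With 34 per arm and 0.69 SD, the three bandings disagree on significance in about 28% of trials (28-29% across separate runs).

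**A caution on the two-band figure.** With exactly 34 per arm, a median split of 21 v 13 gives chi-square = 68 x (21² - 13²)² / 34⁴ = 3.76, p = 0.052. The next split, 22 v 12, gives 5.88, p = 0.015. The test therefore rejects in only about 2.8% of trials when there is no difference, and part of its shortfall comes from this discreteness. The two-band power is about 60% with 33 per arm and 64-65% with 35. The fair summary is roughly 52-65%, depending on the bands and the exact number.

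**What an estimate would give.** The 95% CI half-width for a difference in means, in SD units, is t(0.975, 2n - 2) x √(2/n):

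- 34 per arm: 1.997 x 0.2425 = 0.484 SD
- 49 per arm: 1.985 x 0.2020 = 0.401 SD

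**The 6-month application.** Let q be the share of SDF children who receive it, and assume that both applications cost the same. Mean SDF cost is then proportional to 1 + q. Counting the baseline application alone understates it by q/(1 + q): 50% at q = 1, 33% at q = 0.5 and 17% at q = 0.2. The documents do not give q.

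**The case against.** The strongest reply is that Section 10 names a test without ruling out an estimate. Sections 7.2 and 7.4 plan to calculate and compare cost, and a plan that calculates cost for each intervention would normally yield a difference. A reader might infer from the chi-square sentence that no cost difference will ever be reported; the documents do not support that. What stands is that no estimator or interval is specified, and that the one named test does not suit the variable.

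A second reply is that the power figures rest on an effect size that nothing in the documents supports, and on normal, equal-SD costs for two very different procedures. That is fair. At 1.5 SD every test exceeds 99%, so power is not the main loss. The dependence on undefined bands and the missing estimate do not rely on those assumptions.

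A third reply concerns time capture. A reader might infer that SDF cost will be understated, and by at least a third. Neither inference is supported. The case report forms are not in the text available, and the 6-month form may hold time fields. Sections 4.1, 7.2 and 7.4 speak of regimens, interventions and strategies, and Section 5.2 repeats the same procedure at 6 months, so the second application could be costed from baseline data. Nor is one third a floor. Under Section 6, after a minor or major failure, "the subject will be withdrawn from the study and teeth will be given the appropriate treatment". Failures at or before 6 months could take q below one half. Equal cost is also doubtful, because Table 1 places consent and questionnaires in the baseline visit. This part is a query.

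**Conclusion.** The point holds for the choice of analysis. Section 10 gives overall cost a test that needs undefined bands and returns neither a difference nor an interval, and no other section supplies an estimator. As written, the plan does not answer its relative cost-effectiveness objective. That conclusion rests on the text alone.

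The size of the banding effect is illustrative and holds only under the stated assumptions: about 28% disagreement between bandings, and chi-square power of roughly 52-65% with 33 to 35 per arm against about 80% for means.

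Whether the 6-month application is costed cannot be settled from these documents. The objective is secondary, and nothing here affects the primary failure analysis or the sample size. The sponsor should make the change, but the trial's main conclusion does not depend on it.

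**What to change.** In Section 10, remove overall cost from the chi-square sentence and add: *Cost per child (chair time and materials of the assigned regimen over 12 months) will be compared as the between-arm difference in mean cost with a bootstrap or Welch 95% CI, reported beside the difference in failure proportions.* Name one of the two interval methods in advance; neither requires normal costs with equal SD.

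As a query on Sections 7.3 and 7.4, confirm that the 6-month form records the time and materials of the second SDF application, or that the costing includes them by another stated route. If neither is so, add the entry.

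The cost is a wording change and, at most, one time and materials entry at the 6-month SDF visit, with slight extra recording by the residents. No treatment, visit or sample size changes.
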